- **Risks of ketosis:** Risks of the very low carbohydrate diet include the development of elevated ketone levels. These will be monitored frequently in the outpatient setting and all supplies will be provided to participants. Participants will also be educated on warning signs of DKA and will be instructed to call the study team for any elevated ketone levels  $> 1$  mmol/L or if they have symptoms of ketosis (nausea, vomiting, headache). If a participant develops DKA, they will be withdrawn from the study. Hyperglycemic events will be classified as diabetic ketoacidosis (DKA) if all of the following are present:
  - Symptoms of polyuria, polydipsia, nausea, or vomiting;
  - Serum ketone level  $> 1.5$  mmol/L or large/moderate urine ketones;
  - Serum bicarbonate  $< 15$  or venous pH  $< 7.24$  or arterial pH  $< 7.3$ ;
  - Treatment provided in a healthcare facility;
- **Risk of loss of confidentiality:** As in any study, there is the potential for loss of confidentiality. Female subjects of childbearing potential will require urine pregnancy testing prior to enrollment in the protocol, and results of this testing have potential to result in loss of confidentiality.
- **Risk of glycemic deterioration:** It is possible that changing dietary requirements or insulin doses may result in glycemic deterioration. Likewise, adolescents may have glycemic deterioration due to non-compliance. During the study, dose adjustments will be made according to standard of care to prevent hypoglycemia and hyperglycemia.
- **Risk of CGM:** Participants have the option of using FDA approved CGM as part of clinical care in our clinics. There is a low risk of developing a local skin infection at the site of the sensor needle placement. Itchiness, redness, mild bleeding, and or bruising may occur at the insertion site. Subjects may develop localized reactions to adhesive used to secure the sensor.
- **Risk of study questionnaires:** Participants may experience some distress when discussing factors important to diabetes, diabetes management, and psychosocial stressors

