#### Minimizing Risks:

- **Risks of Very Low Carbohydrate Diet:** In order to minimize the symptoms associated with transitioning to a low carbohydrate diet abruptly, participants will be encouraged to stay hydrated to help them acclimate and avoid unwanted symptoms.
- **Hypoglycemia/Hyperglycemia:** Participants will be contacted frequently during the course of the study. Blood draws will be done frequently during the HRU/CSRJU/Masonicare admission to minimize hypoglycemia and hyperglycemia. Intravenous glucose will be available in case hypoglycemia occurs. All infusates containing insulin are prepared under a filtration cabinet (Laminated HLDA filter) by qualified personnel using sterile disposable materials.
- Participants will be encouraged to monitor closely for signs of glycemic deterioration and will be able to contact our diabetes staff at any time if concerns arise.
- At the end of each visit, the participant will receive guidance for glucose monitoring, food intake, and insulin dosing as needed.
- During the study, insulin doses will be adjusted regularly (2-3 times per week as needed) to prevent hypoglycemia. Participants will use a real-time CGM that will provide alerts at the time of hypoglycemia and allow for early detection of hypoglycemia as well. Participants will be trained on treatment of hypoglycemia and to contact the study team immediately in any case of severe hypoglycemia.
- If any participant has 2 episodes of severe hypoglycemia, they will be transitioned to a regular diet after the 2nd episode of severe hypoglycemia.
- **Stable isotopes:** Isotopes will be carefully monitored, administered and will be prepared in the investigational pharmacy to ensure proper technique. As noted in

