### **5.3 Study Population**

Participants will be youth ages 12 and <25 with a diagnosis of type 1 diabetes for at least 1 year and have an A1c level < 10%. Participants will be recruited from the Yale Pediatric Diabetes Center and Yale Diabetes Center. Participants will also be recruited from ClinicalTrials.gov and social media (Facebook, Twitter, Instagram). The Yale Pediatric Diabetes Center Clinics, which sees over 1000 pediatric patients each year. Of those, 425 patients are between the ages of 12 and 18 with type 1 diabetes each year. It is estimated that 255 (60%) in this age group have an A1c level of < 10% and will be eligible for the study. Based on this information, 85 potential participants are seen each month in our clinics. We anticipate being able to recruit at 10% (8-9 participants) of these patients each month, which is more than enough to complete the study. All participants will undergo pre-screening of their electronic medical record to evaluate study eligibility by review of age and previous laboratory tests. Flyers will also be distributed in the clinics. Participants who meet eligibility criteria may also be contacted by MyChart. Patients who have already completed the study will be contacted about follow up interviews that will be voice-recorded over zoom.

**5.4 Number of Participants:** 20 total participants will be needed to complete the study.

**5.4.1 Eligibility Criteria/Vulnerable Populations:** The principal investigator ([name]) will determine eligibility and inclusion/exclusion criteria.

In order to be eligible to participate in this study, an individual must meet all of the following criteria:

1. Provision of signed and dated informed consent form by the adult (if person is at least 18 years old) or parent and assent form if the participant is <18 years old.
2. Stated willingness to comply with all study procedures and availability for the duration of the study
3. Male, female, transgender, nonbinary are all eligible
4. Ages 12 to <25 years, inclusive, of all races/ethnicities
5. Diagnosis of type 1 diabetes for at least 1 year
6. Hemoglobin A1c level < 10% within the past 2 months
7. Insulin pump use for at least 2 months.
8. Ability to perform daily blood ketone checks, wear a continuous glucose monitor, willing to wear an activity monitor, willing to adhere to the study diets and keep a diet journal.

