### 6.4.2 Sample Size Considerations

For all aims, we base our sample size on the unadjusted comparison of paired means, which is a conservative approach. Therefore, given that our statistical analyses will be based on adjusted models and models that specifically take into account within-person correlation in outcomes of interest, we should be sufficiently powered to answer our research questions.

Aim 1: The goal time in range in adolescents with T1D 60% +/- 10% of their time in the target range of 70-180 mg/dL but based on our preliminary work in this population we expect that the mean percent of time in range is around 50-55%. With 16 eligible subjects, we will have 80% power at the two-sided alpha of 0.05 to detect a minimum increase in the expected mean by 7.5% (from 50-55% on standard carbohydrate diet to 57.5-62.5% on low carbohydrate diet - an increase of 1.5 hours per day - an effect size of  $7.5\% \div 10\% = 0.75$ ), using a paired-sample t-test. If we assume 20% attrition, we will need 20 individuals for the study.

Aim 2: Using data from a previously published study, where changes in glucagon levels during 2-step euglycemic-hypoglycemic clamp in youth with T1D were assessed over a period of 1 year(15), we anticipate that with 16 subjects (n=20 with 20% attrition, see aim 1) we will have 80% power at the two-sided alpha of 0.05 to detect a between-diet change in mean glucagon levels of at least 9.5 pg/mL (standard deviation=12.5 pg/mL, effect size of  $9.5 \text{ pg/mL} / 12.5 \text{ pg/mL} = 0.75$ ), using a paired t-test. We will also report the incremental rise and area under the curve (AUC) as well as mean and peak glucagon levels.

Aim 3: Using estimates of variability (standard deviations [sd]=5 during euglycemia and sd=10 during hypoglycemia) from a previous study, with 16 subjects (20 subjects with 20% attrition) we will have 80% power at the two-sided alpha of 0.05 to detect an effect size in the range of 0.75-1.0, using a paired t-test, meaning that when on low carbohydrate diet, subject

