## 6.5 Planned Analyses

### 6.5.1 Primary Objective Analysis

- **Statistical Analyses Aim 1:** The unadjusted between-diet-group comparison of the primary endpoint, percent time in the target range of 70-180 mg/dL during the 2nd week of each diet, will be performed using a two-sided paired t-test. The adjusted analysis will be performed using linear mixed effects (LME) modeling, with a random intercept for each subject, diet effect, and adjusting for a participant's age, BMI and duration of diabetes. The mean adjusted between diet-group difference in percent time in the target range will be reported, along with the surrounding 95% confidence intervals based on 500 bootstrapped samples (2.5th percentile and 97.5th percentile of the distribution). Secondary outcomes, including time spent with hypoglycemia (<54 mg/dL, <70 mg/dL) and hyperglycemia (>180 mg/dL, >250 mg/dL), average sensor glucose level, will be analyzed similarly to the primary outcome. The proportion of days with elevated fasting  $\beta$ -hydroxybutyrate levels ( $\geq 0.6$  mmol/L) during each diet period will be compared using paired-proportions z-test in the unadjusted analysis and using generalized linear mixed effects (GLMM) modeling (a random intercept, link=logit for the binary outcome yes/no elevated levels with Bernoulli distribution) with covariates of age, BMI, and duration of diabetes. GLMM will also be utilized in the comparison of the number of episodes of diabetic ketoacidosis and severe hypoglycemic events during each period (a random intercept, link=log for a count outcome with Poisson distribution). Statistical analyses for all aims will be implemented using R and SAS 9.4 (Cary, NC) statistical software. Statistical significance will be established at the two-sided alpha of 0.05.

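### The Poisson GLMM planned for DKA and severe hypoglycemia has about 0.77 person-years per diet, so it is likely to give no finite diet comparison, and no rule covers zero counts

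*Combined protocol and SAP*

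**What the plan says.** Section 6.5.1 (Primary Objective Analysis) states that "GLMM will also be utilized in the comparison of the number of episodes of diabetic ketoacidosis and severe hypoglycemic events during each period". The model is specified as "a random intercept, link=log for a count outcome with Poisson distribution", and significance is set at two-sided 0.05. No expected rate, minimum event count, exact or penalised alternative, or rule for zero counts is given.

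The same events also appear as a reported outcome in the Synopsis (Primary Outcome Variables), section 5.2.1 and the table in section 6.2.1. All three promise the number of episodes in the baseline, diet and washout periods, without intervals or time at risk.

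Section 5.4 says "20 total participants will be needed to complete the study", and section 6.1.2 sets each diet at two weeks. Two rules affect who stays under observation. Section 3.2.1 says "If a participant develops DKA, they will be withdrawn from the study". Its part on minimizing risks says "If any participant has 2 episodes of severe hypoglycemia, they will be transitioned to a regular diet" after the second episode.

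**The concern.** A log-link Poisson model estimates the diet effect as a log rate ratio. If one diet has events and the other has none, the likelihood keeps rising as that log ratio grows. Software then stops at an arbitrary large value with a huge standard error, and a Wald test returns a p-value near 1 whatever the data show. If neither diet has an event, there is no diet effect to fit.

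DKA and severe hypoglycemia are the most serious harms that the protocol names for outcome reporting, and section 3.2 expects the study to inform safety considerations and dietary recommendations. A failed model, or an uninformative p-value, would stand where the useful statement should be: how large a risk the data still allow.

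**Working it through.** **The plan's own figure.** Section 6.4.2 says "With 16 eligible subjects, we will have 80% power at the two-sided alpha of 0.05". The difference it targets is 7.5 percentage points with SD 10, so an effect size of 0.75. The noncentral t distribution gives 80.06% power for a paired t-test at n = 16. Section 6.4.2 adds "If we assume 20% attrition, we will need 20 individuals for the study", and 16 / (1 − 0.20) = 20. The figure reproduces, but it covers paired means only and says nothing about event counts.

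**Exposure.** Per diet: 20 × 14 / 365.25 = 0.767 person-years. With 16 participants: 16 × 14 / 365.25 = 0.613.

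**Chance of an empty diet.** Event rates are not in the documents, so a range is assumed, equal on both diets. Expected events per diet are m = rate × 0.767. Under Poisson counts, P(at least one diet with no events) = 1 − (1 − e^−m)², and P(no events on either) = e^−2m.

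| Rate per person-year (assumed) | m | At least one diet empty | Both empty |
|---|---|---|---|
| 0.05 | 0.038 | 99.9% | 93% |
| 0.1 | 0.077 | 99.5% | 86% |
| 0.2 | 0.153 | 98.0% | 74% |
| 0.33 | 0.253 | 95.0% | 60% |
| 0.5 | 0.383 | 89.9% | 46% |
| 1 | 0.767 | 71.3% | 22% |
| 2 | 1.533 | 38.5% | 5% |

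The 95% threshold is 0.33 per person-year with 20 participants and 0.41 with 16.

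**Sensitivity.** If the very low carbohydrate rate is three times the standard-diet rate, the chance of an empty diet is 98.5%, 89.8% and 72.4% at standard-diet rates of 0.1, 0.3 and 0.6. Gamma frailty between participants (shape 0.5 or 0.2) changes little: 95.2–95.3% at 0.3 and about 72% at 1.

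**What the model does with an empty diet.**
- A fixed-effect Poisson fit with one event against none gave a log rate ratio of 20.4 with SE about 16,200. With two against none the SE was about 11,500. With all counts zero the fit failed.
- The random intercept does not rescue it. The random-intercept Poisson likelihood was evaluated by quadrature for 20 participants and two diets, without covariates. With three participants having one event each, all on one diet, the profile log-likelihood was −10.77 at log rate ratio 0, −9.07 at 2, −8.71 at 5 and −8.69 at 12. It rises towards a ceiling and has no finite maximum. One and two events behaved the same way.

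**What an exact comparison can do.** Given k events in total, all on one diet, with equal exposure, the two-sided exact conditional p-value is 2 × 0.5^k. For k = 5 this is 0.0625; for k = 6 it is 0.031. So at least 6 events, all on one diet, are needed for p < 0.05. With equal rates, the chance of 6 or more events over both diets is about 0.001% at 0.3 per person-year and 0.5% at 1.

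**What an exact bound can say.** With zero of n participants affected, the one-sided 95% upper limit is 1 − 0.05^(1/n): 13.9% for n = 20 and 17.1% for n = 16, as a two-week risk.

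**The case against.** The strongest reply is that the result depends on rates the documents do not give. That stands. An empty diet is near certain only up to about 0.33 events per person-year, and at 2 per person-year it is the less likely outcome. This matters most for severe hypoglycemia, which the text supplied neither defines nor gives a rate for.

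A second reply is that counts per period are already promised in three places, so the events will be visible whatever the model does. That also stands. A reader might infer that the safety analysis as a whole yields nothing usable, especially as section 6.5.3 (Safety) is marked N/A. The documents do not support that: the counts survive, and the analyses of time below range, beta-hydroxybutyrate and counterregulatory hormones in 6.5.1 and 6.5.2 are unaffected. What the counts lack is an interval and a denominator.

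Third, section 6.5.1 does not prescribe Wald tests. A likelihood-ratio test of three events against none gives p = 0.041 and a finite lower bound on the rate ratio of about 1.1. This is correct, but the approximation is poor at such counts: the exact p-value for the same data is 0.25.

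Three further inferences should not be drawn:
- That the random-intercept variance can never be identified with an empty diet. With counts of 2 and 1 on one diet and zeros elsewhere, the likelihood has an interior maximum at an SD of about 1.7.
- That the withdrawal and switching rules by themselves defeat the Poisson model. At low rates, repeat events in one person are rare, so a cap on them matters little.
- That the two-episode rule truncates only the very low carbohydrate diet. It refers to any participant, names no arm, and does not say whether a regular diet is the study's standard diet.

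Finally, an exact comparison has almost no power either. That is true, so the gain lies in the bound for each diet and not in a better test.

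**Conclusion.** The concern holds for the model-based diet comparison of DKA and severe hypoglycemia. With about 0.77 person-years per diet, the specified model is likely to have no finite estimate at any assumed rate up to 1 per person-year (71% or more), and almost certain to have none at 0.33 or below (95% or more). It should not be called almost certain without stating the rate. The figures assume Poisson counts, 20 participants completing both two-week diets, and equal rates; the three-fold and frailty checks do not change the picture at low rates.

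These are secondary outcomes and the primary analysis is untouched. The change is still worth making before analysis, because the specified method fails in the likely case and the simple alternative does not.

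**What to change.** In section 6.5.1, replace the Poisson GLMM for these two outcomes with:

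1. The counts already promised, by diet and by period, with the number of participants affected and the days at risk. Participants who are withdrawn or switched contribute up to that point.
2. An exact confidence bound for each diet, reported also when the count is zero: Clopper-Pearson for participants affected, or exact Poisson for the rate.
3. An exact conditional comparison between diets only if events occur, labelled descriptive, with a note that at least 6 events all on one diet are needed for two-sided p < 0.05.

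This needs a paragraph of SAP text and a few lines of code, and changes nothing in trial conduct. It gives up a covariate-adjusted rate ratio, which the data are unlikely to support.

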### 6.5.2 Secondary Objectives Analyses

- **Statistical Analysis Aim 2:** Appropriate mathematical transformations (e.g., natural log or square root) will be applied to each outcome of interest, as necessary, to normalize the distribution. A paired t-test will be used in the unadjusted comparison of the primary outcome, mean levels of glucagon, during each diet period. LME will be used to model the trajectories of change in mean levels of glucagon over time (baseline, 15, 30, 45, 60 minutes) during each diet period and compared between diets. We will use the Likelihood Ratio Test (LRT, a mixture of two chi-square distributions with restricted maximum likelihood – RML - estimation) to select between an LME model with just a random intercept or an LME with a random intercept and slope. The mean response will be modeled using parametric (linear and polynomial effects of time) and semi-parametric (piece-wise linear or quadratic splines) effects of time, adjusting for participants' age, BMI, and duration of diabetes. The best model will be chosen based on its fit to the data (LRT for nested models and Akaike Information Criterion, AIC, for not-nested models).

Effect sizes will be reported as the between-diet differences with bootstrapped 95% CIs. Secondary outcomes of interest will also be modeled similarly.

- **Statistical Analysis Aim 3:** Using the validated Edinburgh Hypoglycemia Symptom questionnaire, participants will be asked to verbally rate their hypoglycemia symptoms on a 7-point Likert scale (lower scores indicate fewer symptoms) during the euglycemia and hypoglycemia portions of the clamp. In the unadjusted analyses, differences between euglycemic and hypoglycemic total scores on each diet will be compared using a paired t-test. Adjusted analyses will be based on LME, similar to the analyses described in Aims 1 and 2. In the secondary analysis, we will model mean hypoglycemia awareness score by domain (e.g., autonomic, neuroglycopenic, and malaise).

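### Choosing the Aim 2 time shape from the trial data can raise the false-positive rate of the between-diet trajectory comparison to about 6.5–12%, depending on choices the plan leaves open; the paired t-test on mean glucagon is unaffected

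*Combined protocol and SAP*

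**What the plan says.** All references are to the combined protocol and SAP.

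For Aim 2, section 6.5.2 first fixes a simple comparison: "A paired t-test will be used in the unadjusted comparison of the primary outcome, mean levels of glucagon, during each diet period". It then turns to mixed models for glucagon at baseline, 15, 30, 45 and 60 minutes, to be compared between diets. On the shape over time it says: "The mean response will be modeled using parametric (linear and polynomial effects of time) and semi-parametric (piece-wise linear or quadratic splines) effects of time", adjusted for age, BMI and diabetes duration. No polynomial degree and no knots are given. The selection rule is "The best model will be chosen based on its fit to the data", using a likelihood ratio test (LRT) where candidates nest and AIC where they do not.

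Whether to add a random slope, and whether to transform the outcome, are also decided from the data. Between-diet differences are then reported with bootstrapped 95% intervals. The section ends: "Secondary outcomes of interest will also be modeled similarly". Section 5.2.1 lists cortisol, epinephrine, norepinephrine and beta-hydroxybutyrate among those outcomes. Section 6.5.1 sets the error rate: "Statistical significance will be established at the two-sided alpha of 0.05".

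The plan does not say whether the candidates contain diet-by-time terms, which diet contrast is read from the chosen model, or whether the bootstrap repeats the selection.

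**The concern.** When candidate shapes carry diet-by-time terms, AIC or the LRT can favour a shape because those terms happen to fit noise that separates the two diets. Testing the same terms in the winner, at the nominal level, uses the data twice. With about 16 participants there is little information to protect against this.

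At stake is the comparison of glucagon trajectories, which bears directly on the section 4.1 hypothesis of an amplified glucagon response on the very low carbohydrate diet. The same holds for the other hormones, for each of which a different time shape could be chosen. With a handful of scheduled sampling times no curve search is needed, because time can enter as categories.

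**Working it through.** **1. The plan's own figure.** Section 6.4.2 states for Aim 2 that "we will have 80% power at the two-sided alpha of 0.05 to detect a between-diet change in mean glucagon levels", with 16 evaluable participants, a difference of 9.5 pg/mL and an SD of 12.5 pg/mL. The effect size is 9.5/12.5 = 0.76, stated as 0.75. For a paired t-test the noncentrality is d√n:

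- d = 0.75: 0.75 × √16 = 3.00; with 15 df and critical value 2.131, power is 80.1%.
- d = 0.76: 0.76 × 4 = 3.04; power is 81.1%.
- Attrition: 16/(1 − 0.20) = 20.

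The figure reproduces, and it belongs to the paired t-test. The plan states no error rate for the trajectory model.

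**2. Set-up of the null simulation.** From the plan: 16 participants, two diets, five times, two-sided 0.05. Assumed: between-subject SD 10, residual SD 6, complete data, no diet effect, and a true time curve that is flat, linear or saturating. There are eight candidates: linear, quadratic, cubic, quartic, piecewise-linear with a knot at 15, 30 or 45 minutes, and a quadratic spline with a knot at 30 minutes. All are random-intercept models fitted by ML. There were 20,000 to 40,000 trials per scenario, so the Monte Carlo standard error near 0.05 is at most √(0.05 × 0.95/20,000) = 0.0015.

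One reading of the plan's rule was coded as follows: LRT steps from linear to quadratic to cubic, then comparison with the two splines with a knot at 30 minutes, by LRT where nested and AIC otherwise.

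**3. Rejection rates under no diet difference.**

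| Selection | Test read | Flat | Linear | Saturating |
|---|---|---|---|---|
| LRT plus AIC, diet-by-time in every candidate | joint diet | 0.070 | 0.069 | 0.065 |
| same | diet-by-time | 0.077 | 0.074 | 0.067 |
| AIC over 8 shapes, diet-by-time in every candidate | joint diet | 0.100 | 0.097 | 0.081 |
| same | diet-by-time | 0.113 | 0.110 | 0.088 |
| same | difference at 60 min | 0.069 | 0.068 | 0.060 |
| same | mean difference | 0.052 | 0.052 | 0.051 |
| AIC also choosing the interaction structure | joint diet | 0.122 | 0.120 | 0.117 |
| AIC, diet as main effect only | diet | 0.052 | 0.052 | 0.051 |
| None: paired t-test on the mean | mean difference | 0.049 | 0.051 | 0.049 |

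With one shape fixed in advance, the joint test rejected in 0.035 to 0.053. Another run, with AIC over eight diet-by-time shapes, gave 10.0% (flat) and 7.7% (saturating), against 4.7–5.1% for categorical time.

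**4. Why the mean difference is safe.** In this balanced design the estimate is the average over participants of (1/5)Σ(Y on one diet − Y on the other), whichever time shape is fitted. The search cannot move it.

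**5. Fixing the shape is not enough.** Let τ be the SD of a subject-by-diet effect, which the plan does not mention. Take a categorical-time model with only a random intercept, and the difference in the mean of the four 15–60 minute values:

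- True variance per participant: 2τ² + 2 × 36/4 = 2τ² + 18.
- The model pools 15 df with mean square 36 + 5τ² and 120 df with 36, and uses 2/4 of the pooled value.
- τ = 4: pooled (15 × 116 + 120 × 36)/135 = 44.9. Model variance is 22.4 against a true 50. The critical value 1.978 shrinks to 1.978/√(50/22.4) = 1.32, giving about 19% rejection.
- τ = 2: pooled 38.2. Model variance is 19.1 against a true 26. 1.978/√(26/19.1) = 1.70, giving about 9%.

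Simulation (20,000 trials) gave 19.1% and 9.0%, and 4.9% at τ = 0. The paired t-test stayed at about 5% throughout.

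**6. Bootstrap.** Assuming that the 500-sample percentile interval of section 6.5.1 also applies to Aim 2, the interval for the 60-minute difference (flat and linear curves) excluded zero in about 0.11 of trials after selection. With a fixed linear shape it did so in 0.084–0.093. Most of that excess comes from the percentile bootstrap at n = 16, not from selection.

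**The case against.** The strongest reply is that the Aim 2 primary outcome has a fixed analysis. The paired t-test on mean glucagon involves no time shape, and the sample size is built on it. This stands, and it limits the point. It does not remove it: section 6.5.2 calls that test the unadjusted comparison, section 6.4.2 says the analyses will rest on adjusted models, and the only trajectory comparison comes from the selected model.

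A second reply is that the plan names no joint or interaction test, and that with a diet main effect there is no inflation. The first half is true, and the size is conditional for that reason. But a main-effect model forces parallel curves, so it cannot compare trajectories of change. The stated purpose points to diet-by-time terms.

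Two stronger readings are tempting. A reader might infer that selection doubles the error rate. Rates of that size arise only when AIC searches many diet-by-time shapes and the joint or interaction test is read; the coded reading of the plan's LRT-plus-AIC rule gives about 1.3 to 1.5 times nominal. A reader might also infer that restricted likelihood will be used to compare mean models, which would be invalid. The text attaches it to the choice between random-effects structures, where it is appropriate. For the mean models the plan names no estimation method, which is a gap and not an error.

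**Conclusion.** The point holds in limited form. The plan states a data-driven rule for the trajectory model and leaves open the choices that determine its error rate. For the joint or diet-by-time comparison, the false-positive rate after selection is about 6.5–8% under one reading of the LRT-plus-AIC rule and about 8–12% under wider AIC searches, against about 5% with one prespecified shape. For a diet main effect or the mean between-diet difference, selection adds nothing. The documents do not support a reading in which the main Aim 2 test on mean glucagon is compromised.

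These figures rest on assumed variance components, time curves, knots and polynomial degrees, complete data, and a correctly specified random intercept. The data-driven choices of transformation and random slope were not simulated. The covariates were also left out; they are essentially constant within a participant and should not move the diet contrast. If there is subject-by-diet variation, a random-intercept model can exceed 5% by more than selection does, so the remedy must cover the covariance as well as the mean.

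**What to change.** In section 6.5.2:

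- Replace the selection step with one prespecified model: diet, time as categories and diet-by-time, with a subject-by-diet (clamp-level) random effect or an equivalent within-clamp covariance.
- Name one 1-df contrast: the between-diet difference in the mean of the 15–60 minute hypoglycemia values, tested on participant-level differences or in that model.
- Define baseline and reconcile the sampling times. The Synopsis and 5.2.1 give 15, 30, 45 and 60 minutes for both phases. Section 6.2.1 gives 15–30 minute intervals in the first euglycemic step. Section 6.3.5 lists 0, 30, 45 and 60 minutes for euglycemia, and elsewhere hormone samples every 5–10 minutes late in each phase. Section 6.5.2 uses a baseline that it does not define.
- Keep splines for figures only. If any selection is retained, compare mean models by ML and repeat the selection inside each bootstrap sample.
- Apply the same model to the other serially sampled hormones.

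The cost is SAP wording, with no change to sample size or visits. The model carries a few more time parameters, and the multi-df interaction test has somewhat less power than a correctly chosen simple curve would give. The 1-df contrast loses nothing.
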